3.1.3. Use of Antipyretic/Pain Medication

Antipyretic/pain medications used to treat symptoms are recorded in the e-diary. This variable will be presented along with the systemic event summary, but not counted as a systemic event. The following variables will be derived:

1. Use of antipyretic/pain medication on “any day (Days 1-14)” after vaccination.
2. Duration of use of antipyretic/pain medication after vaccination.
3. Onset day of antipyretic/pain medication use after vaccination.

3.1.4. Adverse Events

AE reporting will be based on the specific reporting period. Standard algorithms for handling missing AE dates and missing AE severity will be applied as described in the Pfizer Vaccine data standard rules.

As this is a Phase 1/2 study, with limited sample size included in each vaccine group, the value of applying the 3-tier approach is limited. Therefore, because of a small number of subjects in each dose/formulation group, safety assessment may be best carried out using descriptive statistics.

For AEs within 1 month after each vaccination, the interval calculation will be based on the study visit. Table 7 includes all AE intervals for each cohort. Any AEs with start date occurring within the lower bound and upper bound (inclusive) are included in the interval. It should be noted that Visit 2 and Visit 8 include intramuscular vaccination, thus AEs with start date at Visit 2 should be included in the next interval (AEs within 1 month after Vaccination 2). For consistency, this is applied to all intervals.

Table 7. AE Analysis Interval

Cohort	Interval	AE Start Date Lower Bound (Inclusive)	AE Start Date Upper Bound (Inclusive)
Sentinel cohort	AEs within 1 month after Vaccination 1	Visit 1	The day before Visit 3
Expanded cohort	AEs within 1 month after Vaccination 1	Visit 1	The day before Visit 2 ^a
Expanded cohort	AEs within 1 month after Vaccination 2	Visit 2	The day before Visit 3
CCI			

a. This visit includes a vaccination.

The following derivations/summaries will be included for each of the above:

1. Proportions of subjects reporting AEs during this interval summarized for each system organ class and preferred term (and “any event”), separately.
2. Proportion of subjects reporting any AE during this interval.
3. Proportion of subjects reporting any MAE during this interval.
4. Proportion of subjects reporting any SAE during this interval.
5. Proportion of subjects reporting any related AE during this interval.
6. Proportion of subjects reporting any severe AE during this interval.
7. Proportion of subjects reporting any intermediate AE. Intermediate AE is defined as an AE reported within the first 30 minutes after vaccination.
8. Proportion of subjects reporting any AE leading to withdrawal during this interval.

3.1.5. Medically Attended Adverse Events

MAEs are collected after the AE collection period. Any MAEs with start date occurring within the lower bound and upper bound (inclusive) are included in the interval. Table 8 describes how the MAE analysis intervals are determined by study visits in each cohort. The following MAE-related variables will be derived:

1. Proportion of subjects reporting any MAE during this interval.
2. Proportions of subjects reporting MAEs during this interval summarized for each system organ class and preferred term, separately.

Table 8. MAE Analysis Interval and Derivation

Cohort	Interval	Start Date Lower Bound	Start Date Upper Bound
Sentinel cohort	MAEs through 12 months after Vaccination 1	Visit 1	Visit 7
Expanded cohort	MAEs through 12 months after Vaccination 1	Visit 1	Visit 6
CCI			

3.1.6. Serious Adverse Events

SAEs are collected throughout the study. Any SAEs with start date occurring within the lower bound and upper bound (inclusive) are included in the interval. Table 9 describes how the SAE analysis intervals are determined by study visits in each cohort. The following SAE-related variables will be derived:

1. Proportion of subjects reporting any SAE during this interval.
2. Proportions of subjects reporting SAEs during this interval summarized for each system organ class and preferred term, separately.

Table 9. SAE Analysis Interval and Derivation

Cohort	Interval	Start Date Lower Bound	Start Date Upper Bound
Sentinel cohort	SAEs through 12 months after Vaccination 1	Visit 1	Visit 7
Expanded cohort	SAEs through 12 months after Vaccination 1	Visit 1	Visit 6
CCI			

3.2. Secondary Endpoint(s)

Sentinel Cohort:

- RSV A– and RSV B–neutralizing antibody titers measured before Vaccination 1 and 2 weeks and 1, 2, 3, and 6 months after Vaccination 1.

Expanded Cohort:

- RSV A– and RSV B–neutralizing antibody titers measured before Vaccination 1 and 1, 2, 3, and 6 months after Vaccination 1.
- Hemagglutination inhibition assay (HAI) titers for all strains in the SIIV measured before and 1 month after SIIV administration.

3.2.1. RSV A– and RSV B–Neutralizing Antibody Titers

RSV A– and RSV B–neutralizing antibody titers will be determined on all sera collected at applicable visits for antibody testing.

Titers above the lower limit of quantitation (LLOQ) are considered accurate and their quantitated values will be reported. Refer to Section 5.3.2 for LLOQs. Titers below the corresponding LLOQ or denoted as below the limit of quantitation (BLQ) will be set to $0.5 \times \text{LLOQ}$ for analysis. Missing assay results will not be imputed.

In addition to titer, the neutralizing titer (NT) fold rise from before vaccination to each time point after the vaccination will be derived for both RSV A and RSV B as detailed below:

1. For the sentinel cohort: NT fold rise will be derived from before Vaccination 1 to each time point after Vaccination 1 with NT assay performed (2 weeks and 1, 2, 3, 6, and 12 months after Vaccination 1).
2. For the expanded cohort: NT fold rise will be derived from before Vaccination 1 to each time point after Vaccination 1 with NT assay performed (1, 2, 3, 6, and 12 months after Vaccination 1).

CCI

For calculating a fold rise, $< \text{LLOQ}$ will be converted to $\frac{1}{2} \text{LLOQ}$ for a numerator, and $< \text{LLOQ}$ will be converted to LLOQ for a denominator when only one of either the numerator or denominator is $< \text{LLOQ}$. If both the numerator and denominator are $< \text{LLOQ}$, then both will be converted in the same way.

3.2.2. HAI Titers

Hemagglutination inhibition antibody titers will be measured by the standard HAI for the 4 influenza vaccine strains contained in the SIIV. The assay will have LLOQ = 1:10 for each strain.

For the expanded cohort: HAI fold rise will be derived from before SIIV to 1 month after SIIV for each strain tested. The visit numbers will be different for the different vaccine groups.

- For subjects in the coadministration groups (RSV vaccine and SIIV at Visit 1), the fold rise will be the ratio of Visit 2 to Visit 1.
- For subjects in the sequential-administration groups (SIIV after RSV vaccine, or SIIV at Visit 2), the fold rise will be the ratio of Visit 3 to Visit 2. If Visit 2 data are not available, Visit 1 data will be used.

In addition to the HAI titer and HAI fold rise, 2 binary variables will be derived for each of the influenza strains tested:

1. HAI seroprotection before and after SIIV vaccination: HAI titer is $\geq 1:40$.
2. HAI seroconversion after SIIV vaccination:
 - a. If the HAI titer is $< 1:10$ (LLOQ for HAI) before SIIV administration, seroconversion is achieved if the postvaccination titer is $\geq 1:40$.
 - b. If the HAI titer is $\geq 1:10$ before SIIV administration, seroconversion is achieved if the fold rise from the pre-SIIV titer to the postvaccination titer is ≥ 4 .

The pre-SIIV and post-SIIV data have similar visit assignments as the fold-rise derivation.

CCI [REDACTED]

[REDACTED]

[REDACTED]

[REDACTED]

[REDACTED]

CCI [REDACTED]

[REDACTED]

| [REDACTED]

| [REDACTED]

[REDACTED]

| [REDACTED]

| [REDACTED]

| [REDACTED]

[REDACTED]

| [REDACTED]

[REDACTED]

| [REDACTED]

| [REDACTED]

| [REDACTED]

[REDACTED]

| [REDACTED]

| [REDACTED]

| [REDACTED]

| [REDACTED]

[REDACTED]

[REDACTED]

C [REDACTED]
I [REDACTED]

I [REDACTED]

I [REDACTED]

I [REDACTED]

[REDACTED]

I [REDACTED]

CCI [REDACTED]

[REDACTED]

[REDACTED]

[REDACTED]

[REDACTED]

[REDACTED]

[REDACTED]

[REDACTED]

[REDACTED]

[REDACTED]

[REDACTED]

CCI [REDACTED]

[REDACTED]

[REDACTED]

[REDACTED]

[REDACTED]

[REDACTED]

CCI [REDACTED]

[REDACTED]

[REDACTED]

[REDACTED]

[REDACTED]

[REDACTED]

[REDACTED]

[REDACTED]

[REDACTED]

[REDACTED]

CCI [REDACTED]

[REDACTED]

[REDACTED]

[REDACTED]

[REDACTED]

[REDACTED]

[REDACTED]

CCI [REDACTED]

[REDACTED]

[REDACTED]

[REDACTED]

[REDACTED]

[REDACTED]

[REDACTED]

[REDACTED]

[REDACTED]

[REDACTED]

1
|

[REDACTED]

[REDACTED]

[REDACTED]

[REDACTED]

[REDACTED]

[REDACTED]

[REDACTED]

[REDACTED]

[REDACTED]

[REDACTED]

[REDACTED]

[REDACTED]

[REDACTED]

[REDACTED]

[REDACTED]

[REDACTED]

[REDACTED]

[REDACTED]

3.5. Baseline Variables

3.5.1. Baseline Definition

Day 1 is defined as the day of vaccination and start of the reporting period for local reactions and systemic events in the e-diary.

3.5.2. Demographics, Smoking History, and Medical History

Demographic variables collected include sex, race, ethnicity, and date of birth. Age at the time of vaccination (in years) will be derived based on birthday. For example, if the vaccination date is 1 day before the subject's 19th birthday, the subject is 18 years old.

Medical history of clinical significance will be collected and categorized according to the current version (at the time of reporting) of the Medical Dictionary for Regulatory Activities (MedDRA).

Subject smoking history is also collected before Vaccination 1.

3.6. Safety Endpoints

Additional safety endpoints not covered in Section 3.1 and details of safety endpoints derivation are described in this section.

3.6.1. Laboratory Data

Blood samples for hematology and blood chemistry assessments (approximately 10 mL) will be collected for all sentinel-cohort subjects at Visit 0 and Visit 2.

Assessments will include:

- Hematology: hemoglobin, complete blood count with differential, and platelets.
- Blood chemistries: alanine aminotransferase (ALT), aspartate aminotransferase (AST), alkaline phosphatase, total bilirubin, blood urea nitrogen (BUN), and creatinine.

The grade change from Visit 0 to Visit 2 for each laboratory assessment will be derived. This should include all combinations of grading between the 2 visits. For example:

1. Within normal range to Grade 1
2. Remaining normal
3. Remaining Grade 1
4. Grade 1 to within normal range

3.7. Study Conduct

3.7.1. E-Diary Completion

An e-diary will be considered transmitted if any data for the local reactions, systemic events, or use of antipyretic/pain medication are present for any day. If all data are missing for all items on the e-diary for all 14 days (local reactions, systemic events, and use of antipyretic/pain medication) after vaccination, then the e-diary will be considered not transmitted. An e-diary will be considered transmitted for a given day if any data are present for that day.

3.7.2. Nonstudy Vaccines

Any nonstudy vaccinations given will be recorded in the CRF from the signing of the informed consent (ICD) to the 12-month follow-up visit (Visit 7 for sentinel-cohort subjects, Visit 6 for expanded-cohort subjects), ^{CCI} [REDACTED]

Nonstudy vaccines will be categorized according to the latest version (at the time of reporting) of the World Health Organization (WHO) Drug Dictionary.

4. ANALYSIS SETS

Data for all subjects will be assessed to determine if subjects meet the criteria for inclusion in each analysis population prior to unblinding and releasing the database, and classifications will be documented per standard operating procedures.

Three analysis populations (evaluable RSV immunogenicity population, modified intent-to-treat [mITT] population, safety population) and the fourth analysis population (additional evaluable influenza immunogenicity population, as detailed below) will be defined for each of the [REDACTED] analysis cohorts: sentinel cohort, expanded cohort, combined sentinel and expanded cohorts. ^{CCI} [REDACTED]

The evaluable immunogenicity population will be the primary analysis population for the immunogenicity endpoints evaluated for each cohort. Subjects will be included in the vaccine group as randomized in the analysis, which, by the population definition, is equivalent to the vaccine group corresponding to the vaccine received.

Analysis of immunogenicity results based on the mITT population will be considered supportive and will be performed only for critical endpoints, such as secondary endpoints, if there is enough difference (eg, >10%) between the evaluable immunogenicity population and the mITT population.

The safety population will be used for all analyses related to safety endpoints.

4.1. Sentinel Cohort

This cohort will include a total of 7 groups (6 vaccine groups and placebo), and 3 analysis populations will be defined. The placebo group will pool all subjects who were randomized or received placebo within each dose cohort.

4.1.1. Evaluable RSV Immunogenicity Population

This evaluable immunogenicity population will include subjects from the sentinel cohort who:

- Are eligible (have signed informed consent and met all inclusion/not met any exclusion criteria) and were randomized into the study;
- Have received RSV vaccine or placebo as randomized;
- Have a Visit 3 (1 month after vaccination) blood draw for assay testing within 27 to 42 days after Visit 1, inclusive, after vaccine administration (note: the 27- to 42-day interval is calculated as the Visit 3 date minus the Visit 1 date);
- Have at least 1 valid and determinate assay result for the 1-month postvaccination visit;
- Have no major protocol violation as determined by the study clinician.

Major protocol violations will be determined by clinical review. A major protocol violation is a protocol violation that, in the opinion of the sponsor's study medical monitor, would materially affect assessment of immunogenicity, eg, subject receipt of a prohibited vaccine or medication that might affect immune response or a medication error with suspected decrease in potency of the vaccine. The sponsor's medical monitor will identify those subjects with protocol violations before any immunogenicity analysis is carried out.

4.1.2. mITT Population

All randomized subjects in the sentinel cohort who have at least 1 valid and determinate assay result related to the proposed analysis will be included in the mITT population.

4.1.3. Safety Population

All subjects in the sentinel cohort receiving at least 1 dose of the investigational products at Visit 1 will be included in the safety population. For the safety analyses, subjects will be analyzed according to the vaccine as administered.

4.2. Expanded Cohort

This cohort will include a total of 13 groups (12 vaccine groups and placebo), and 4 analysis populations will be defined.

4.2.1. Evaluable RSV Immunogenicity Population

This evaluable immunogenicity population will include subjects from the expanded cohort who:

- Are eligible (have signed informed consent and met all inclusion/not met any exclusion criteria) and were randomized into the study;
- Have received the vaccine (RSV vaccine or placebo) at Visit 1 as randomized;
- Have a Visit 2 (1 month after Vaccination 1) blood draw for assay testing within 27 to 42 days after Visit 1, inclusive, after vaccine administration (note: the 27- to 42-day interval is calculated as the Visit 2 date minus the Visit 1 date);
- Have at least 1 valid and determinate assay result for the 1-month postvaccination visit;
- Have no major protocol violation as determined by the study clinician.

4.2.2. Evaluable Influenza Immunogenicity Population

This evaluable immunogenicity population will include subjects from the expanded cohort who:

- Are eligible (have signed informed consent and met all inclusion/exclusion criteria) and were randomized into the study;
- Have received the 2 vaccines (RSV vaccine or placebo with SIIV) at Visit 1 as randomized;
- Have received influenza vaccine at Visit 1 or Visit 2;
- Have a blood draw for assay testing within 27 to 42 days, inclusive, after influenza vaccination (note: the 27- to 42-day interval is calculated as the blood draw date minus the SIIV vaccination date. Refer to Section 3.2.2 for the corresponding visits based on the different vaccine groups);
- Have at least 1 valid and determinate assay result 1 month after influenza vaccination;
- Have no major protocol violation as determined by the study clinician.

This population will be the primary analysis population related to influenza assay results.

4.2.3. mITT Population

All randomized subjects in the expanded cohort who have at least 1 valid and determinate assay result related to the proposed analysis will be included in the mITT population.

4.2.4. Safety Population

All subjects in the expanded cohort receiving at least 1 dose of the investigational products at Visit 1 will be included in the safety population. For the safety analyses, subjects will be analyzed according to the vaccine as administered.

4.3. Combined Sentinel and Expanded Cohorts

This cohort will pool subjects from the sentinel cohort and expanded cohort. Only subjects who are randomized to receive SIIV at Visit 2 from the expanded cohort will be pooled with the sentinel cohort, across the dose/formulation groups. This cohort will include a total of 7 groups (6 vaccine groups and placebo), and 3 analysis populations will be defined.

4.3.1. Evaluable RSV Immunogenicity Population

This evaluable immunogenicity population will include subjects from the combined sentinel and expanded cohorts who:

- Are eligible (have signed informed consent and met all inclusion/not met any exclusion criteria) and were randomized into the study;
- Have received the vaccine (RSV vaccine or placebo) at Visit 1 as randomized;
- Have 1-month post-Vaccination 1 blood drawn for assay testing within 27 to 42 days after Visit 1, inclusive, after vaccine administration (note: the 27- to 42-day interval is calculated as the blood draw date minus the vaccination date);
- Have at least 1 valid and determinate assay result for the 1-month postvaccination visit;
- Have no major protocol violation as determined by the study clinician.

4.3.2. mITT Population

All randomized subjects in the combined sentinel and expanded cohorts who have at least 1 valid and determinate assay result related to the proposed analysis will be included in the mITT population.

4.3.3. Safety Population

All subjects in the in the combined sentinel and expanded cohorts receiving at least 1 dose of the investigational products at Visit 1 will be included in the safety population. For the safety analyses, subjects will be analyzed according to the vaccine as administered.

CCI

[REDACTED]

[REDACTED]

[REDACTED]

[REDACTED]

[REDACTED]

[REDACTED]

[REDACTED]

[REDACTED]

[REDACTED]

[REDACTED]

[REDACTED]

[REDACTED]

[REDACTED]

[REDACTED]

[REDACTED]

[REDACTED]

[REDACTED]

[REDACTED]

[REDACTED]

[REDACTED]

CCI

5. GENERAL METHODOLOGY AND CONVENTIONS

5.1. Hypotheses and Decision Rules

5.1.1. Statistical Hypotheses

This Phase 1/2 FIH study is designed to describe the safety, tolerability, and immunogenicity of RSV vaccine formulations in 2 age groups. No formal statistical hypothesis testing will be performed. An estimation approach will be used to assess the safety and immunogenicity objectives.

5.1.2. Statistical Decision Rules

Statistical decision rules will not be utilized in this study. All analyses are considered descriptive in nature.

5.2. General Methods

Safety data and immunogenicity data will be summarized by vaccine group for each cohort. All analyses will be descriptive in nature.

Unless otherwise stated, “95% CI” refers to 2-sided 95% CI in this document.

5.2.1. Analyses for Binary Data

Descriptive statistics for binary variables are the proportion (%) and the numerator (n) and the denominator (N) used in the proportion calculation. The 95% CI for percentage, and for difference in percentages, will also be presented, where appropriate.

1. The 95% CI for the proportion will be constructed by the Clopper-Pearson method described by Newcombe.³ The 95% CI will be presented in terms of percentage.
2. The 95% CI for the difference in the proportions will be computed using the Miettinen and Nurminen method.⁴ The 95% CI will be presented in terms of percentage.

5.2.2. Analyses for Continuous Data

Unless otherwise specified, descriptive statistics for continuous variables are n, mean, median, standard deviation, minimum, and maximum.

The CI for the mean of the continuous variable will be constructed by the standard method based on Student’s t distribution.

5.2.2.1. Geometric Mean Titer

Continuous immunogenicity endpoints will be logarithmically transformed for analysis. Geometric mean titer (GMT) and associated 95% CI will be calculated at each available time point for each vaccine group and cohort. Geometric means and their 95% CIs will be derived by calculating means and CIs on the natural log scale based on the t distribution, then exponentiating the results.

5.2.2.2. Geometric Mean Fold Rise

Geometric mean fold rises (GMFRs) will be limited to subjects with nonmissing values at both visits. Individual subject antibody levels fold rise from one time point to another time point will be transformed in natural logarithm scale for analysis. Means and their 95% CIs on the natural log scale will be based on the 1-sample Student's t distribution. GMFRs and corresponding 95% CIs will be calculated by exponentiating the results from the natural log scale.

5.2.2.3. Geometric Mean Ratio

The geometric mean ratio (GMR) will be calculated by transforming the group mean difference of the antibody levels in natural logarithm scale to original scale. 95% CI is also computed by exponentiating the CIs from the natural log scales using 2-sample Student's t distribution for the mean difference of measures on the logarithmically transformed assay results.

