2.2. Study Design

This is a Phase 1/2, randomized, placebo-controlled, observer-blind, dose-finding first-in-human (FIH) study.

The study will evaluate the safety, tolerability, and immunogenicity of up to 6 RSV vaccine candidates with CCI [REDACTED] at 3 escalating dose levels of 60 µg CC [REDACTED] 120 µg CC [REDACTED] and 240 µg CCI [REDACTED] of the prefusion RSV F antigen, with or without aluminum hydroxide (Al[OH]₃), when administered alone or concomitantly with SIIV.

This study will utilize a sentinel cohort (Phase 1) and an expanded cohort (Phase 2) for each dose level in each age group. The age groups will run in parallel but independently from each other.

In the sentinel cohort (Phase 1), subjects will be enrolled into 2 age groups with equal numbers of subjects:

- Male and female subjects 18 to 49 years of age.
- Male and female subjects 50 to 85 years of age.

In the expanded cohort (Phase 2), subjects will be enrolled into 2 age groups with equal numbers of subjects:

- Male and female subjects 18 to 49 years of age.
- Male and female subjects 65 to 85 years of age.

In the sentinel cohort, approximate 168 subjects will receive a single intramuscular dose of the RSV vaccine candidate with or without Al(OH)₃ or placebo at Vaccination 1. Central randomization will take place in a 3:3:1 ratio for each dose level, by age stratum.

In the expanded cohort, 1014 subjects will be randomized equally across all dose/formulation levels, with or without SIIV, by age group via center-based randomization. This will include a total of 13 groups with an equal randomization ratio. Subjects in this cohort will receive 2 intramuscular injections at Visit 1 (Vaccination 1) and 1 intramuscular injection at Visit 2 (Vaccination 2). CCI [REDACTED]

CCI
[Redacted]

For both sentinel-cohort and expanded-cohort subjects, key safety data include electronic diary (e-diary) reports of local reactions and systemic events that occur within 14 days after Vaccination 1 (RSV vaccine or placebo). Adverse events (AEs) are collected from informed consent until 1 month after Vaccination 1 (Visit 3 for the sentinel cohort); and from consent until 1 month after Vaccination 2 (Visit 3 for the expanded cohort). AEs occurring up to 48 hours after blood draws are also collected. Medically attended AEs (MAEs) are collected after the AE collection period. Serious adverse events (SAEs) are being collected for all subjects from informed consent through 12 months after Vaccination 1.

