6. ANALYSES AND SUMMARIES

This section describes the analyses and summaries across all endpoints. In order to reconcile the protocol-specified endpoints (or estimands) and SAP template structure, the primary endpoints and secondary endpoints specified in the protocol are carried out in the “primary analysis” described in this section.

CCI

For each of the analysis sets (sentinel cohort, expanded cohort, combined sentinel and expanded cohorts), all safety and immunogenicity endpoints listed below will be summarized by age stratum, without combining the total age range. For the combined sentinel and expanded cohorts, the older age group will use a sentinel-cohort age range of 50 to 85 years.

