6.2.2.2. Additional Summary

The seroprotection rate before SIIV (Visit 1 or 2) and 1 month after SIIV, and seroconversion rates from before SIIV to 1 month after SIIV, will be summarized with n, percentage (%), and 95% CI, among the expanded cohort.

The following comparisons will be made in order to assess the interference of RSV vaccine coadministration with the SIIV immune response (expanded cohort only):

- For each RSVpreF dose/formulation, 1-month post-SIIV GMTs from the SIIV coadministration group will be compared with SIIV administered after the same RSVpreF dose/formulation, for each influenza strain tested. GMRs and associated 95% CIs will be calculated.
- For each RSVpreF dose/formulation with SIIV coadministration, 1 month post-SIIV GMTs will be compared with the control group that had SIIV administered after placebo, for each influenza strain tested. GMRs and associated 95% CIs will be calculated.
- For each RSVpreF dose/formulation with SIIV coadministration, 1-month post-SIIV GMTs will be compared with the pooled group without coadministration of RSVpreF (including the control group that had SIIV administered after placebo, and SIIV administered after RSVpreF) for each influenza strain tested. GMRs and associated 95% CIs will be calculated.

The evaluable influenza immunogenicity population will be used. However, the mITT population may be used for some comparison.

CCI
[Redacted]

[Redacted]

[Redacted]

CCI [Redacted]

[Redacted]

CCI [Redacted]

[Redacted]

[Redacted]

[Redacted]

CCI [Redacted]

[Redacted]

[Redacted]

[Redacted]

[Redacted]

[Redacted]

[Redacted]

CCI

[Redacted]

[Redacted]

CCI

[Redacted]

[Redacted]

[Redacted]

[Redacted]

[Redacted]

CCI

[Redacted]

[Redacted]

[Redacted]

[Redacted]

[Redacted]

[Redacted]

CCI [REDACTED]

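### The variance assumption behind the GMR interval is not stated; it matters only for the pooled HAI contrast (about 39 v 273 per age stratum), where an unequal-variance t interval is the safer choice

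*SAP*

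**What the plan says.** SAP section 5.2.2.3 is the only place that defines the GMR interval. The limits are back-transformed from the natural log scale and rest on the 2-sample Student's "t distribution for the mean difference of measures on the logarithmically transformed assay results". The section does not name a variance estimator or degrees of freedom, and does not mention Welch or Satterthwaite.

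Section 6.2.2.2 lists three HAI comparisons for interference with the SIIV response. Two set one group against one group. In the third, each coadministration group's post-SIIV "GMTs will be compared with the pooled group without coadministration of RSVpreF", a comparator described as "including the control group that had SIIV administered after placebo, and SIIV administered after RSVpreF".

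The group sizes follow from the design. Section 2.2 says that "1014 subjects will be randomized equally across all dose/formulation levels, with or without SIIV, by age group via center-based randomization", and adds: "This will include a total of 13 groups with an equal randomization ratio". Section 4.2 gives the make-up: "This cohort will include a total of 13 groups (12 vaccine groups and placebo"). The age groups are of equal size (section 2.2), and section 6 says that endpoints "will be summarized by age stratum, without combining the total age range".

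Sections 5.1.1 and 5.1.2 rule out formal testing and decision rules and take an estimation approach. The SAP gives no SD for HAI titers.

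**The concern.** Two-sample Student's t ordinarily means the equal-variance interval. With equal group sizes that interval is robust to unequal SDs. At 1:7 it is not: the pooled variance comes almost entirely from the large group, while the true standard error is driven by the small one. If the SDs differ, the interval is too narrow when the small arm is the more variable and too wide when it is the less variable.

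Equal SDs cannot be taken for granted here. One side is a single arm, and the other mixes a placebo arm with six dose/formulation arms.

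With no test and no margin, the interval is what a reader has for judging precision. The pooled contrast yields 4 strains × 6 dose/formulations × 2 age strata = 48 such intervals. The text also leaves room for two programmers to produce different limits from the same data.

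**Working it through.** **Group sizes**

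- Per group and age stratum: 1014 / 13 / 2 = 39 (sections 2.2 and 4.2).
- The 12 vaccine groups are 6 dose/formulations, each with SIIV at Visit 1 or at Visit 2. The pooled comparator is therefore the 6 sequential RSVpreF groups plus the placebo group: 7 × 39 = 273.
- The contrast is 39 v 273 as randomized. Evaluable numbers will be somewhat lower.

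**Formulas.** Set the pool's SD of ln titer to 1 and the coadministered arm's SD to r. The SAP gives no SDs, so r is an assumption. Coverage depends only on r and the group sizes.

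- Expected pooled variance: (38r² + 272) / 310
- Standard error the pooled method uses: √[pooled variance × (1/39 + 1/273)]
- True standard error: √(r²/39 + 1/273)
- Approximate coverage: 2Φ(1.968 × SE used / true SE) − 1, where 1.968 is the 97.5% point of t on 310 df

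**The plan's own figure.** At r = 1 the two standard errors agree (0.1712), and simulation gives 94.95% coverage. This reproduces the nominal 95%.

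**Worked example, r = 1.25.** The pooled variance is (59.375 + 272) / 310 = 1.069. The SE used is √(1.069 × 0.02930) = 0.1770, and the true SE is √(0.04006 + 0.00366) = 0.2091. Their ratio is 0.846, and 1.968 × 0.846 = 1.665, so coverage is about 90.4%.

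**Results at 39 v 273** (simulation of normal ln titers, 400,000 replicates per row)

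| SD ratio r (coadministered/pool) | SE used / true SE | Formula | Simulated, pooled variance | Simulated, Welch |
|---|---|---|---|---|
| 0.80 | 1.181 | 98.0% | 98.0% | 95.0% |
| 0.90 | 1.082 | 96.7% | 96.6% | 95.0% |
| 1.00 | 1.000 | 95.1% | 95.0% | 95.0% |
| 1.10 | 0.931 | 93.3% | 93.3% | 95.0% |
| 1.25 | 0.846 | 90.4% | 90.3% | 95.0% |
| 1.50 | 0.742 | 85.6% | 85.6% | 95.0% |

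With 35 v 245 evaluable the pooled-variance results are almost the same: 90.3% at 1.25 and 85.4% at 1.50.

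**The 39 v 39 contrasts.** With equal sizes the expected pooled variance, (r² + 1)/2, times 2/39 equals the true (r² + 1)/39. The standard errors therefore agree for every r. Simulated coverage is 94.9% to 95.0% for r from 0.5 to 2.0. This covers every contrast in section 5.2.2.5, the RSV interference GMRs in section 6.2.1.2 and the first two HAI comparisons in section 6.2.2.2.

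**Effect of mixing seven arms.** Assume equal within-arm SDs, with the seven arm means differing by a between-arm SD of 0.1, 0.25 or 0.5 within-arm SDs. Simulated pooled-variance coverage is then 95.1%, 95.5% and 97.0% (100,000 runs each). Mixing raises the pool's SD, puts r below 1 and makes the interval too wide.

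**Cost of Welch at r = 1.** The mean half-width is 0.3422 v 0.3365 SD units, a ratio of 1.017. The df are about 50 instead of 310.

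**The case against.** The strongest reply is that the SAP never says the variances are pooled. Section 5.2.2.3 names a reference distribution, and a Welch interval also uses a t distribution. Section 2 says that programming rules are prepared separately, so the option may be set there. This stands: the fault is an unstated assumption with a default reading, not a demonstrated error.

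A reader might infer that any difference in SD spoils the interval. It does not. A 5% difference moves coverage by less than 1 percentage point and a 10% difference by less than 2. The error becomes material at an SD difference of roughly 20% to 25%.

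A reader might also infer that the mixed comparator makes the interval too narrow. It works the other way, as the seven-arm simulation shows. Under-coverage of 90% or 86% needs a coadministered arm 1.25 or 1.5 times as variable as the pool. The SAP gives no reason to expect that, and none to exclude it.

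Finally, one might read this as a threat to the interference assessment as a whole. Section 5.2.2.5, which is devoted to interference, contains no pooled contrast, and the two other HAI comparisons in section 6.2.2.2 are 39 v 39 and unaffected. With no margin or decision rule, no formal conclusion turns on these limits. That objection also stands.

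What remains is that the plan takes an estimation approach, so the stated confidence level should hold. For this one contrast it depends on an assumption that the plan neither states nor supports.

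**Conclusion.** The point holds in a limited form and is a cheap improvement. Section 5.2.2.3 leaves the variance assumption open, and under its usual reading the interval for the pooled HAI contrast is sensitive to unequal SDs. Coverage runs from about 98% at an SD ratio of 0.8 to about 86% at 1.5.

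These figures rest on assumed SD ratios, normal ln titers and the randomized sizes of 39 v 273. The documents do not establish that a material SD difference exists, or its direction. The consequence is misstated precision in one supplementary, descriptive comparison. It is not a wrong decision, and it does not touch the one-group-v-one-group GMRs.

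**What to change.** State in section 5.2.2.3 that the confidence interval for the difference in mean ln titer uses the unequal-variance (Welch-Satterthwaite) 2-sample t interval, at least for the pooled HAI contrast in section 6.2.2.2. Applying it to all GMRs is simpler and changes the 39 v 39 intervals by less than 1% (mean half-width ratio at most 1.006 for SD ratios from 0.5 to 2.0).

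The cost is one sentence and one software option. If the SDs are in fact equal, the pooled-contrast intervals become about 2% wider on the ln scale. In return, simulated coverage stays at 94.9% to 95.0% for SD ratios from 0.5 to 2.0, and the text no longer allows two different computations.
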